## 7 STATISTICS

### 7.1 Sample size calculation

In order to use the win-odds method for a non-inferiority study we performed more than 1000 simulations using the statistical software R. We used the primary variables listed in 6.1 to calculate our sample size and assumed that the outcomes are independent and that the outcomes were equally distributed among study arms (i.e. we simulated a win-odds of 1.0). We set the power of the study to 80% with a lower limit of confidence interval for win-odds (also called non-inferiority limit) to above 0.60 and calculated a sample size of 150 individuals divided into two treatment arms. We set the possible number of dropouts until the 2-year follow-up to 20%, and the total sample size therefore adjusted to 180 individuals.

**7.1.1** What is a non-inferiority limit. The non-inferiority limit is the probability of a patient in the active arm (minimally invasive procedure) to win over a control patient given an evenly distributed number of ties [6].

**7.1.2** In the case that the MIS group shows slight benefits compared to the open surgery group then the non-inferiority limit will shift towards 1.0 as the win odds will be greater than 1.0 which was assumed in the sample size simulation.

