## SYNOPSIS

### **Rationale for conducting the study:**

The operative treatment of idiopathic scoliosis typically involves a posterior correction with fixation by open surgery with simultaneous fusion of the operated levels. That type of surgery, although it leads to an almost anatomical correction, involves a long hospitalization time due to extensive tissue damage and pain. Recently, however, by using various regimes such as "ERAS" (enhanced recovery after surgery), including optimization of pain relief, inpatient stay times have been heavily reduced, and discharge as early as 1-2 days after surgery is now possible to achieve.

In recent years, there has been a development of minimally invasive techniques in spine surgery where tissue damage and blood loss are significantly minimized. It is of importance to scientifically investigate whether the use of minimally invasive techniques also in scoliosis surgery results in benefit for patients.

We need to investigate whether minimally invasive techniques are comparable to traditional open surgery in terms of reoperations, serious adverse events, infections, pain and radiologically healed fusion. One complexity of minimally invasive surgery (MIS) lies in the correct placement of implants in the deformed spine while preserving the tissue and not exposing the anatomical landmarks that usually guide for correct screw placement. It is why MIS practically entails the use of intraoperative 3D imaging or robotic assisted surgery (RAS) to improve screw placement accuracy.

The aim with this project is to evaluate whether MIS is non-inferior to the traditional open technique regarding reoperations, serious adverse events, infections, pain and radiologically healed fusion. At the same time, we want to compare the aforementioned techniques regarding inpatient stay, degree of correction, screw placement, neurophysiological incidences, blood loss, operation time, and patient related outcomes (PROMs).

As of yet, the majority of data in this area are based on retrospectively collected series, and some prospectively collected series, while randomized controlled trials are lacking.

**Study design:** Multicenter randomized controlled clinical trial.

**Study population:** Individuals with spinal deformity aged 10 through 25 years.

**Number of individuals:** 180

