## 4.4 Discontinuation and withdrawal of subjects

Subjects are free to discontinue their participation in the study at any time. This will not affect further treatment. Patients will be withdrawn from study if the patient withdraws consent. Already collected study data for these patients will be kept in the study database, however new data, including data from registries will not be added.

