## 5.7 Surgical data and complications

Detailed surgical data will be collected through hospital files, radiographs, Swespine or similar platforms. Additional spine surgeries (diagnosis and type of surgical procedure) will be identified in Swespine (or similar platforms) and the hospital files. Adverse events (postoperative infection, deep vein thrombosis and pulmonary emboli) will be collected from the hospital files and Swespine.

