## 5.8 Imaging

Normal imaging and time points are as follows: Standard preoperative investigations include a whole spine standing radiograph, a whole spine bending radiograph and magnetic resonance imaging (MRI) of the spine. A preoperative low-dose CT or an intraoperative CBCT is always performed prior to screw placement. Screw placement is verified by a CBCT intraoperatively. The minimum radiologic follow-up includes a whole spine standing radiograph at the 3-month follow-up and a low-dose CT along with a standing radiograph at the 2-year follow-up. Curve size, type of scoliosis and other radiological parameters will be registered.

Clinical Study Protocol	Unique protocol ID	MISCOS
	Version No:	1.1
	Date:	2025-09-27

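### Section 7.1 adds 20% to 150 to reach 180, but losing 20% of 180 leaves 144; 180 keeps 150 only up to 16.7% dropout

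*Protocol*

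**What the plan says.** Protocol section 7.1 links three figures. From simulations at 80% power, with a true win odds of 1.0 and a non-inferiority limit of 0.60, the authors "calculated a sample size of 150 individuals divided into two treatment arms". They then allow for losses: "We set the possible number of dropouts until the 2-year follow-up to 20%, and the total sample size therefore adjusted to 180 individuals". The synopsis repeats the total: "Number of individuals: 180".

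No inflation formula is printed. No other dropout rate is given and no replacement of dropouts is described. Section 5.5 ends inclusion when the sample size is reached in both arms and does not tie this to completers.

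Three other sections bear on what a dropout can still contribute:

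- Section 4.4 keeps data already collected when consent is withdrawn, but "new data, including data from registries will not be added".
- Section 5.7 says that additional spine surgeries "will be identified in Swespine (or similar platforms) and the hospital files".
- Section 5.8 schedules "a low-dose CT along with a standing radiograph at the 2-year follow-up", the imaging from which fusion would be read. Section 2.1 (primary endpoint) also places NRS back pain and SRS-22r at 2 years.

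**The concern.** A dropout rate is normally a share of the patients enrolled. To keep n evaluable patients after losing a fraction d, one enrols n / (1 − d). Section 7.1 instead appears to have used n × (1 + d), which always gives too few.

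At stake is whether the planned total secures the number behind the stated 80% power at the plan's own dropout rate. It also matters for reporting: sample-size text is usually carried into the publication, and a reader can check this sentence in one line.

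**Working it through.** **Inputs**, all from Protocol section 7.1 except the allocation ratio:

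- Required number before dropout: 150 in total, so 75 per arm at 1:1 (section 5.5).
- Dropout until 2 years: 20%.
- Stated total: 180 (also in the synopsis).
- Stated power: 80%.

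The 150 itself is taken as given. Section 7.1 does not print the event rates or the confidence level used in the simulation.

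**Reproducing the plan's figure.** n × (1 + d) = 150 × 1.20 = 180. This matches exactly.

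**Applying the stated dropout to the stated total.**

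- Lost: 180 × 0.20 = 36.
- Remaining: 180 × 0.80 = 144, or 72 per arm.
- Shortfall: 150 − 144 = 6, which is 6 / 150 = 4%.

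**Dropout that 180 does tolerate.** (180 − 150) / 180 = 30 / 180 = 16.7%.

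**Total that would hold 150 at 20%.** 150 / 0.80 = 187.5, so 188 (94 per arm), 8 more than planned. Check: 188 × 0.80 = 150.4.

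**Remaining out of 180 by dropout rate**, if dropouts contribute nothing:

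| Dropout | Remaining |
|---|---|
| 10% | 162 |
| 15% | 153 |
| 16.7% | 150 |
| 20% | 144 |

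**Effect on power.** Assume that 150 gives exactly 80%. The standardised distance to the margin scales with the square root of the sample size, so power at 144 is Φ((z + 0.8416) × √(144/150) − z), where z is the critical value of the confidence limit.

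- z = 1.960 (two-sided 95%): 2.8016 × 0.9798 − 1.960 = 0.785, power 78.4%, a loss of 1.6 points.
- z = 1.645 (one-sided 95%): 2.4866 × 0.9798 − 1.645 = 0.791, power 78.6%, a loss of 1.4 points.

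The loss is therefore roughly 1.5 points under either confidence level.

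**Comparison with simulation error.** The Monte Carlo standard error of an 80% power estimate from 1000 runs is √(0.8 × 0.2 / 1000) = 0.0126, or 1.3 points. Section 7.1 says only that more than 1000 simulations were run, so the actual error may be smaller.

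**The case against.** **The 20% may be meant as a share of the 150.** No denominator is printed. Read this way, 30 dropouts are allowed for and 150 + 30 = 180 is consistent. But section 7.1 describes loss up to the 2-year follow-up, which happens among enrolled patients, and 30 of 180 is 16.7%. On this reading the rate still needs restating.

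**Intention to treat keeps everyone in the analysis.** Section 7.2.2 says that patients who drop out or are lost to follow-up stay in their randomised group, so 144 would not be the number analysed. That text stands under the secondary variables. Keeping a patient in the group also does not supply a missing 2-year pain score, SRS-22r or CT. Section 7.1 itself treats dropout as a loss to be made up; otherwise there would be no reason to go from 150 to 180.

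**Dropouts still carry information.** This stands in part. Serious complications, early surgical site infection and inpatient infection mostly arise well before 2 years, and reoperations can be found in registries and hospital files unless consent is withdrawn. So 144 is a lower bound on the effective number. Partial information softens the power loss, but it does not make 20% dropout and 150 retained compatible with 180 enrolled.

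**The true power at 144 cannot be derived from the protocol.** This also stands. A no-ties rank approximation, with standard error of the log win odds √(4/3 × (1/n₁ + 1/n₂)), true win odds 1.0 and margin 0.60, gives 77.3% at 150 and 75.6% at 144 for a two-sided 95% interval, but 85.6% and 84.4% for a one-sided 95% limit. Whether 144 falls below 80% therefore depends on inputs that are not printed. The difference between 150 and 144 is small in both cases: 1.7 and 1.3 points.

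**Conclusion.** The concern holds and is minor. With 20% dropout among those enrolled, 180 leaves 144 and not 150, and the 30 added patients cover 16.7%. Nothing elsewhere in the protocol repairs this, since dropouts are not replaced and recruitment does not continue until 150 have completed.

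The consequence is at most 6 evaluable patients and roughly 1.5 percentage points of power. That rests on two assumptions: dropouts contribute nothing, and 150 gives exactly 80%. The loss is about the size of the simulation error at 1000 runs. It introduces no bias and leaves the type I error unchanged. The arithmetic itself needs no assumption beyond the usual meaning of a dropout rate.

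**What to change.** Keep 180 and correct one figure in section 7.1, in one of two ways:

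- State that 180 tolerates 16.7% dropout (30 of 180) while keeping 150 evaluable.
- Keep the 20% and state that it leaves 144 evaluable in the worst case, with the power re-simulated at 144. If 150 gives just 80%, expect a figure slightly below 80%.

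The cost is one sentence, plus one rerun of the existing simulation for the second option. Either the tolerated dropout or the stated power becomes slightly less favourable. The synopsis and section 5.5 stay as they are.

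Raising the total to 188 would also reconcile the figures, but it is not needed for an effect this small and would not be free. About 50 patients per year (section 3.1) over the three years from mid 2025 to mid 2028 (section 13.1) gives 50 × 3 = 150, already below 180.

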### 7.2 Statistical analysis

#### 7.2.1 Primary variables

We selected the above described seven variables in hierachic order to conduct a win-odds analysis. The variables were selected based on the clinical impact that they have on the patient. The method of win-odds was first introduced as win-ratio [7] in order to analyze composite endpoints based on clinical priorities. The method compares each treatment subject to all controls and the outcome is registered as "win", "lose" or "tie". In order to handle large numbers of ties the win-odds was introduced [8] that assigns 50% of the ties to both the numerator and the denominator. Particularly in non-inferiority trials the use of win-odds instead of win-ratio may be more suitable since ties in non-inferiority studies may represent a comparable treatment effect and their number is substantial [6].

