## **Primary endpoint**

The primary endpoint is the assessment of a group of variables by the statistical method of “win odds”. The variables are in hierachic order:

- i. No reoperations at 2 years after surgery. A reoperation is defined as a secondary surgical procedure related to the index procedure and involving the spine at any level after the index procedure.
- ii. No serious complication related to the procedure. Serious complication is defined as a life-threatening complication or a complication related to substantial invalidity (like pneumothorax or spinal cord injury).
- iii. No early surgical site infection (SSI). Early SSI is defined as SSI with onset up to 12 weeks postoperatively.
- iv. No other infection related to the inpatient stay like pneumonia or urinary tract infection (UTI).
- v. Assessment of pain at 2 years f-u: The numeric rating scale (NRS) for back pain will be used measured on a scale from 0 (no pain) to 10 (worst possible pain). Data will be collected from Swespine or similar platforms.
- vi. Assessment of SRS-22r: The SRS-22r is a scoliosis specific questionnaire aiming to estimate quality of life in patients with scoliosis [1]. It contains 24 items divided into 5 domains covering function, pain, self-image, mental health, and satisfaction. An index value is calculated for each domain and a total index value is possible to calculate ranging from 1 (worst) to 5 (best). SRS-22r will be collected from Swespine or similar platforms at 2 years.
- vii. Radiologically healed fusion at 2 years f-u. A radiologically healed fusion is defined as bone bridging along the originally operated levels. A vertebral segment will be considered fused if one or both of the following conditions is satisfied:
  - a. Bone bridge over at least one facet joint
  - b. Bone bridge between the vertebral bodies

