## 3 STUDY DESIGN AND PROCEDURES

### 3.1 Overall study design and flow chart

This is a multi-center parallel assignment two arm randomized controlled trial (Figure 1). The trial will use a pragmatic approach and use existing equipment and document handling at the participating centers. Data from the existing quality registries for spine surgery will be extracted for outcome assessments.

Randomization between the two treatment arms will take place approximately a week preoperatively, as close to the operation day to minimize selection bias. Postoperative, blinding of the patients and health care personnel will be done.

[figure not shown]
The surgeons will be the only personnel related to patient follow-up that will not be blinded. However, the majority of the analyses, all postoperative imaging and record data collection and analysis will be performed by blinded reviewers.

Patient reported outcomes will be assessed without influence of the care giver.

Clinical Study Protocol	Unique protocol ID	MISCOS
	Version No:	1.1
	Date:	2025-09-27

The Uppsala University hospital performs approximately 80 spine deformity surgeries yearly and it is estimated that  $1/4$  of these meet the inclusion criteria for the study. Similar estimations are done for the rest of the centers with a total enrolment of approximately 50 patients per year. Our time plan includes study start (mid 2025), last patient included (2028) and last 2 year follow up (2029). Registry outcome data are collected preoperatively, at 1 year and 2 years. Registry data may also be collected at 5 and 10 years. The study may have come to an end 2038. However, delays in studies such as these are not uncommon.

Figure 1: Flowchart

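### The primary win odds could be adjusted, at no cost in patients or data, for the SRS-22r score (and perhaps back pain) already collected before surgery

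*Protocol*

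**What the plan says.** The primary endpoint (Protocol section 2.1, repeated in 6.1) is a seven-level hierarchy. Levels i to iv are events: reoperation, serious complication, early surgical site infection and other infection. Level v is back pain: "Assessment of pain at 2 years f-u: The numeric rating scale (NRS) for back pain will be used". Level vi is SRS-22r at 2 years and level vii is radiological fusion. Levels v and vi enter as 2-year values, with no change score or baseline term.

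Section 7.2.1 describes the comparison: "The method compares each treatment subject to all controls and the outcome is registered as 'win', 'lose' or 'tie", with ties split equally. It names no covariate, and it excludes none.

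On baseline data, section 3.1 says: "Registry outcome data are collected preoperatively, at 1 year and 2 years". The footnote to Table 1 lists SRS-22r, EOSQ-24, ODI and EQ-5D as collected before surgery. NRS back pain is not in that list, so only the general sentence in 3.1 could imply it.

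On size, section 7.1 says: "We set the power of the study to 80% with a lower limit of confidence interval for win-odds (also called non-inferiority limit) to above 0.60". This led to 150 evaluable patients, simulated under equal arms ("i.e. we simulated a win-odds of 1.0"), and to 180 in total after an allowance for 20% dropout. No confidence level, event rates, score distributions or baseline-to-2-year correlation are given.

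**The concern.** Non-inferiority is declared when a lower confidence limit exceeds 0.60, so any avoidable variance costs power directly. If the event levels are uncommon, most pairs are settled by 2-year pain and SRS-22r. Part of the spread in those scores was present before surgery and has nothing to do with the operation. In an unadjusted comparison that part acts as noise.

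A baseline measurement collected anyway can remove some of this noise without touching the hierarchy, the margin or the sample size. Adjusted and unadjusted lower limits can also fall on opposite sides of 0.60, so the choice should be fixed before outcomes are seen.

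**Working it through.** **1. How many pairs reach the pain level?** The protocol gives no event rates, so two sets are assumed for levels i to iv, equal in both arms and independent across levels (section 7.1 makes the same two assumptions). A pair ties on a level with event rate p with probability p² + (1−p)².
- Rates 5, 2, 2 and 3% (about 12% of patients with any event): 0.905 × 0.961 × 0.961 × 0.942 = 0.79.
- Rates 10, 3, 4 and 5% (about 20% with any event): 0.820 × 0.942 × 0.923 × 0.905 = 0.65.

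Under these rates, 65 to 79% of pairs go on to the pain and SRS-22r levels.

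**2. The plan's own figure.** Inputs from 7.1: margin 0.60, true win odds 1.0, 75 per arm, power 80%. Assumed: two-sided 95% interval and few ties.
- SE(log WO) = 4·√[(1/12)(1/75 + 1/75 + 1/75²)] = 0.189
- −ln(0.60) = 0.511
- Power = Φ(0.511/0.189 − 1.96) = 77.0%
- N for 80% power = (16/3)(1.960 + 0.842)²/0.511² ≈ 160

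The figure of 150 is not reproduced exactly under these assumptions, but two things the protocol leaves open could account for that:
- With one-sided 0.05, power at 150 is 85.4% and about 126 patients suffice.
- A reduction in variance of 5 to 6.5% through ties gives N = 152 to 150.

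**3. What adjustment does.** Let θ be the win probability with half the ties, so that WO = θ/(1−θ). The adjusted estimate is θ̂ − C′V⁻¹(x̄₁ − x̄₀). Here x̄₁ − x̄₀ is the difference in baseline means, V its covariance matrix and C its covariance with θ̂. The variance is multiplied by (1 − R²) and the SE by √(1 − R²). Closed-form power at a two-sided 95% level:

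| R² | 150 evaluable | 144 evaluable (180 × 0.8) |
|---|---|---|
| 0 | 77.0% | 75.3% |
| 0.05 | 79.1% | 77.5% |
| 0.10 | 81.2% | 79.6% |
| 0.15 | 83.4% | 81.8% |

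**4. What R² is plausible?** R² refers to the whole hierarchy, so the event levels dilute it. The seven levels were simulated with 75 per arm and 3000 runs per setting. Assumptions: integer NRS, SRS-22r to 0.01, fusion 90%, NRS and SRS-22r correlated 0.5, and both preoperative scores available. rho is the baseline-to-2-year correlation.

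| Patients with any level i–iv event | rho | Unadjusted | Adjusted |
|---|---|---|---|
| about 12% | 0.3 | 77% | 79% |
| about 12% | 0.4 | 77% | 81% |
| about 12% | 0.5 | 76% | 82% |
| about 20% | 0.5 | 76% | 80% |

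With rho = 0, power was 76% unadjusted and 77% adjusted. At rho 0.5 the adjusted-to-unadjusted variance ratio was 0.85 and 0.90 for the two event levels, that is, R² of about 0.15 and 0.10, in fair agreement with step 3.

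A separate simulation at 150 evaluable, with low, middle and high event rates, gave gains of 1.6 to 2.6 points at rho 0.3, 1.6 to 4.4 at rho 0.4 and 2.9 to 7.1 at rho 0.5. Monte Carlo error on each power figure is about √(0.76 × 0.24/3000) = 0.8 points.

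**5. If only SRS-22r is available before surgery.** At rho 0.5 and 75 per arm, power goes from 77 to 79% with low event rates and from 75 to 76% with high ones. At 144 evaluable and middle rates it goes from 75.4 to 76.5% at rho 0.4 and from 75.0 to 77.5% at rho 0.5. The gain is small because pain ranks above SRS-22r and its own baseline is then missing. Using the SRS-22r pain domain as a substitute was not simulated.

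**The case against.** The strongest objection is that this belongs in the statistical analysis plan, which is not at hand. Section 7.2.1 explains how a win odds works and rules out no adjustment; an adjusted win odds uses the same all-pairs comparison. An unadjusted win odds is also valid under randomization, and its interval already allows for chance baseline imbalance. All of that stands. A reader might infer that the sponsor has left the baseline data unused; without the analysis plan this cannot be established. What remains is that the one description of the primary comparison at hand is unadjusted, and a more precise estimator can be built from data already collected.

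A reader might also infer that the trial is underpowered and that adjustment would bring it back to 80%. The documents do not support this. The confidence level is not stated, and at one-sided 0.05 power is already about 85% at 150 patients and 84% at 144. Ties, which 7.2.1 expects to be substantial in number in non-inferiority studies, could account for the figure of 150. Nor does adjustment reliably reach 80%: at rho 0.3 it gives 79% in the table above, and with high event rates at 144 evaluable it gives only 79% even at rho 0.6.

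A larger gain, from 77% to 88%, follows if R² is 0.25 for the whole hierarchy. That would need the two scores to decide every pair, which the four event levels ranked above them prevent.

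**Conclusion.** The point holds as an efficiency improvement to a valid analysis. The protocol describes an unadjusted primary win odds while collecting SRS-22r, and possibly NRS back pain, before surgery.

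With a two-sided 95% interval, true win odds 1.0 and 75 per arm, the expected gain is about 1 to 2 points of power from SRS-22r alone and about 2 to 7 points from both baselines at correlations of 0.3 to 0.5. There is essentially no loss if the correlation is zero. The size rests on assumed event rates, correlations and confidence level, and the larger gain also needs a preoperative NRS that the Table 1 footnote does not name. It is not evidence that the 80% in section 7.1 is wrong.

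**What to change.** In section 7.2.1, or in the analysis plan before any outcome is examined by arm, state that:
- the primary win odds is estimated with randomization-based (nonparametric) covariate adjustment for the preoperative SRS-22r total score and, where collected, preoperative NRS back pain, otherwise the preoperative SRS-22r pain domain;
- the adjusted lower confidence limit is the one compared with 0.60;
- missing baseline values receive a simple fill-in blind to arm, such as the overall mean;
- the unadjusted win odds is reported as a sensitivity analysis.

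The cost is a few sentences and a little programming. No patients, visits or data are added, and the hierarchy, margin and sample size stay as they are. It would help to confirm whether NRS back pain is part of the preoperative registry form, since most of the possible gain depends on it.

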#### 7.2.2 Secondary variables

For the secondary variables descriptive statistics will be used to characterize the data; means and 95% confidence intervals will be used for parametric data, medians and interquartile ranges for non-parametric data, and number (proportions) for categorical data. For groups comparisons t-test or ANOVA will be used for parametric distributed data and Wilcoxon, Mann-Whitney or Kruskal-Wallis test will be used for non-parametric distributions respectively, along with post hoc analysis. Categorical data will be compared with Chi-square, McNemar or Sign tests.

Clinical Study Protocol	Unique protocol ID	MISCOS
	Version No:	1.1
	Date:	2025-09-27

Data from the different groups will be compared based on the 'intention to treat' principle. An intention to treat (ITT) analysis means that all patients, regardless of treatment change, loss to follow-up or drop-out, remain in the analysis of the group to which they were randomized. Statistical expertise blinded for treatment allocation will perform the statistical analyses.

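### With no other route for missing data named, pairs left undecided by dropout default to ties, which pulls the win odds towards 1.0 and favours non-inferiority

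*Protocol*

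**What the plan says.** The primary endpoint (protocol 2.1 and 6.1) is a seven-tier hierarchy: reoperation, serious complication, early surgical site infection, other infection, back-pain NRS, SRS-22r and radiological fusion. Reoperation, NRS, SRS-22r and fusion are assessed at 2 years.

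Section 7.2.1 sets each treated patient against all controls and allows three results: win, lose or tie. The win odds "assigns 50% of the ties to both the numerator and the denominator". The section adds that ties in a non-inferiority trial may reflect a comparable treatment effect.

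The intention-to-treat paragraph says that "all patients, regardless of treatment change, loss to follow-up or drop-out, remain in the analysis of the group to which they were randomized". It is printed at the end of 7.2.2 on secondary variables, but its wording is general and no other analysis set is named for the primary endpoint.

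Section 7.1 requires the "lower limit of confidence interval for win-odds (also called non-inferiority limit) to above 0.60", simulated under equal arms ("i.e. we simulated a win-odds of 1.0"). On losses it reads "We set the possible number of dropouts until the 2-year follow-up to 20" per cent, and raises 150 patients to 180. Under section 4.4, data collected before withdrawal are kept and nothing is added afterwards, registry data included.

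No section says how a missing component is scored in a pairwise comparison.

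**The concern.** Take a pair in which one patient has no 2-year NRS, SRS-22r or CT and in which no earlier tier separates the two. Under 7.2.2 the patient stays in. Under 7.2.1 the pair must be a win, a loss or a tie, and nothing in hand makes it a win or a loss. With no imputation or exclusion named, a tie is the only result left.

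In a superiority trial such ties would be conservative. Here they work the other way: each one adds half a win to each side and moves the estimate towards 1.0, away from the 0.60 limit. A patient whose pairs all tie also has a score of exactly one half, which narrows the interval. Worse follow-up would then make the trial easier to pass, and absent data would count as evidence of comparability.

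**Working it through.** **Inputs from the protocol.** Limit 0.60, planned win odds 1.0, power 80%, 150 patients raised to 180, dropout 20% (all 7.1); allocation 1:1 (5.5), hence 90 per arm.

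**Assumed, because not stated.** Two-sided 95% confidence interval, with 90% as the alternative. Missingness is equal in both arms and unrelated to outcome. Component rates for the first simulation: reoperation 5%, serious complication 2%, surgical site infection 3%, other infection 3%, non-fusion 10%, NRS SD 2, SRS-22r SD 0.5.

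**1. The plan's own figure.** Without ties, Var(log win odds) at equal arms is about (16/12)(1/n1 + 1/n2), so total N = (16/3)(zα + zβ)² / (ln 0.60)².
- 95% interval: 5.333 × 7.849 / 0.2609 = 160.
- 90% interval: 5.333 × 6.183 / 0.2609 = 126.

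The stated 150 lies between these. It cannot be reproduced exactly without the confidence level and component rates, but it is plausible: power at 75 per arm is 77% or 85%. The 180 is 150 × 1.2.

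**2. Shift in the win odds if every pair with a missing patient ties.** With a proportion d missing per arm, the share of such pairs is t = 1 − (1 − d)². A true win odds of 0.60 is a win probability of 0.60/1.60 = 0.375. The expected probability is 0.375(1 − t) + 0.5t.

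| d | t | Expected probability | Expected win odds |
|---|---|---|---|
| 5% | 0.0975 | 0.387 | 0.63 |
| 10% | 0.19 | 0.399 | 0.66 |
| 20% | 0.36 | 0.24 + 0.18 = 0.42 | 0.42/0.58 = 0.72 |

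This step needs no component rates. A true value of 1.0 stays at 1.0.

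**3. Narrowing of the interval, equal arms, d = 20%.** An observed patient's score is 0.8U + 0.1, with U roughly uniform; a missing patient's is exactly 0.5. The score variance is 0.8 × 0.64/12 = 0.512/12.
- Missing as ties, 90 per arm: SE of log win odds = 4√(2 × 0.512/(12 × 90)) = 0.123. Chance of passing = Φ(0.511/0.123 − 1.96), about 99%.
- Dropouts left out, 72 per arm: SE = 4√(2/(12 × 72)) = 0.192. Chance of passing = Φ(0.511/0.192 − 1.96), about 76%.

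**4. Simulated chance of declaring non-inferiority, 90 per arm.** In the first simulation the whole difference between arms was placed in NRS and SRS-22r. Its true win odds was about 0.60 (0.606 in the calibration run).

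| Handling of 20% missing per arm | Mean win odds | Passes, 95% interval | Passes, 90% interval | Equal arms, 95% interval |
|---|---|---|---|---|
| All tiers tie | 0.73 | 34% | 44% | 98% |
| Tiers i–iv known, v–vii missing | 0.73 | 29% | 37% | 95% |
| Dropouts left out | 0.60 | 2.4% | 6% | 75% |

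With 10% missing, either tie rule gives a win odds of about 0.67 and about 10% false claims at 95%. A second simulation at a true win odds of about 0.59 gave about 32%, 24% and 2% for the three rows at 95%. The range quoted, 24–34%, spans both simulations and both tie scenarios.

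**The case against.** The strongest reply is that the protocol never scores missing as a tie. Section 7.2.1 describes the method in general terms, and rules for missing components are commonly left to a statistical analysis plan, which may exist. Multiple imputation would satisfy every sentence of 7.2.1 and 7.2.2. This stands in part. The tie is the default reading and not an explicit rule, and silence on missing data alone would be no finding. What remains is that the protocol does fix the analysis set, the three permitted results and the tie split, and following those as written gives a biased answer.

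A reader might also infer that 7.1 contradicts 7.2, because one inflates for dropouts and the other keeps them. The documents do not support this. Inflation allows for lost information and intention to treat fixes group membership; a trial can do both.

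Nor does each missing 2-year value create a tie. Reoperations and complications can be found in hospital files and the registry (5.7, Table 2), data from before withdrawal are kept, and NRS and SRS-22r come from a different source than fusion. Only a pair undecided on everything available is affected. Even so, the simulation with tiers i–iv fully known still gives 24–29%.

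Finally, 20% is a planning allowance and not a forecast. The percentages are conditional on that.

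**Conclusion.** The point holds as a default reading that the protocol should close off. If pairs left undecided by missing data are ties, a true win odds of 0.60 is expected to appear as 0.72 at 20% missing per arm when all tiers tie; this is arithmetic. The chance of a false non-inferiority claim is roughly 24–34% instead of 2.5%. That range rests on a two-sided 95% interval, 90 per arm, missingness equal between arms and unrelated to outcome, and illustrative component rates. It would be lower with less dropout, or if tiers i–iv are known and carry more of the difference between arms.

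A reader might take one of these percentages as the trial's actual type I error. The documents do not support that, since neither the confidence level, the component rates nor the handling of missing components is stated.

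**What to change.** In 7.2.1, state that a pair undecided because of missing data is not scored as a tie. Use observed tiers first. Then multiply impute the missing 2-year components within arm from baseline data, the 1-year registry questionnaires (SRS-22r, ODI, EQ-5D) and any observed 2-year components, and combine the win odds over imputations. Genuine ties in completed data keep the 50/50 split.

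The auxiliary data have limits. CT for fusion is scheduled only at 2 years and back-pain NRS is not listed at 1 year (Table 1, 5.8, 6.2), so both would be imputed from the other variables. ODI is collected only from age 15.

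Add a tipping-point sensitivity analysis that makes imputed outcomes for missing MIS patients progressively worse. Scoring all of them as losses is too severe: with equal arms and 20% of MIS patients missing, the win probability is 0.8 × 0.5 = 0.40, the win odds 0.67, and the lower 95% limit about 0.67 × exp(−1.96 × 0.172) = 0.48. The analysis would usually fail with identical arms.

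State also that the intention-to-treat paragraph covers the primary endpoint.

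The cost is wording and standard imputation code, with no new data collection. The interval will be somewhat wider and the apparent power lower than with missing scored as ties. The change should be made before 2-year data are seen.
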